1 LIST OF ABBREVIATIONS

ADL	Activities of daily living
AE	Adverse event
Alk Phos	Alkaline phosphatase
ALT	Alanine aminotransferase
AST	Aspartate aminotransferase
Beta cells	The predominant type of cell in the islets.
BB-IND	Bureau of Biologics, Investigational New Drug
CA 125	Cancer antigen, marker for ovarian cancer
CA 19-9	Cancer antigen 19-9, specific marker for certain gastrointestinal tumors
CBC	Complete blood count
Cc	Cubic centimeter
cc/min	Cubic centimeter per minute
CD133+	Some melanoma cells contain subset of cells expressing CD133+, a surface antigen
CD44+	Multispecific cell adhesion molecule
Cd16	A cluster of differentiation found on the surface of natural killer cells
CEA	Carcinoembryonal antigen
CT scan	Computerized tomography
CTCAE v3.0	Common Terminology Criteria for Adverse Events
DLT	Dose limiting toxicity
DNA	Deoxyribosenucleic acid
DSMB	Data Safety Monitoring Board
ECOG	Eastern Collaborative Oncology Group
EGFR	Epidermal growth factor receptor/gene
EKG	Electrocardiogram
e-MuLV DNA	Ecotropic murine leukemia virus envelope protein
EORTC	European Organization for Research and Treatment of Cancer
FDA	Food and Drug Administration
G1-S	Stage in the cell cycle at the boundary between the G1 phase and the S phase.
G2-M	Checks for damaged DNA and unreplicated DNA
GADD45	A p53-regulated stress protein
GGT	Gamma glutamyl transpeptidase
GI	Gastrointestinal
GLP	Good Laboratory Practice
GMP	Good Manufacturing Practice
HAMA	Anti-mouse antibodies
HER-2	Human epidermal growth factor receptor
HIV	Human immunodeficiency virus
IgA	Immunoglobulin A
IgE	Immunoglobulin E

IgG	Immunoglobulin G
IgM	Immunoglobulin M
IND	Investigational New Drug
INR	International Normalization Ratio
IRB	Institutional Review Board
IV	Intravenous
kD	KiloDalton
Kg	Kilogram
Ki67	Cell-cycle related nuclear protein; proliferation marker.
LD	Lactic dehydrogenase
mg/dl	Milligram per deciliter
μM	Micromole
MuLV	Murine leukemia virus
Mm	Millimeter
MRI	Magnetic resonance imaging
MTD	Maximum tolerated dose
mTor	Coordinates several upstream signaling pathways in renal tumor cells.
MTT assay	Laboratory test for measuring the activity of enzymes
NCI	National Cancer Institute
NK	Natural killer cell
OS	Overall survival
p27	Gene which lies on chromosome 12 in humans
PCR DNA	Method by which a few fragments of DNA can be duplicated
PET scans	Positron emission tomography
PFS	Progression-free survival
PT	Prothrombin Time
PTT	Partial Thromboplastin Time
RENCA	Renal adenocarcinoma
RT-PCR	Reverse transcription polymerase chain reaction
SAE	Serious adverse event
T cells	A type of blood cell that protects the body from infection.
TPN	Total parenteral nutrition
USPHS	United States Public Health Service
VEGF	Vascular endothelial growth factor

2 BACKGROUND

Treatment for cancer has traditionally consisted of three modalities: surgery, radiation therapy and chemotherapy. Advances with all three modalities over the years have produced some long-term remissions and/or cures in certain types of cancer such as the leukemias, and prolonged survival for many other patients. The advent of targeted, often more “biological” therapies such as tyrosine kinase inhibitors, inhibitors of angiogenesis, inhibitors of, and antibodies to, specific receptors such as mTor, HER-2, VEGF, and EGFR, has further changed the face of anti-cancer therapy. Much remains to be accomplished, however, especially with respect to the treatment of solid tumors, including some of the most common and deadly cancers such as those of the lung, colon, breast, ovary, prostate, pancreas, and kidney. New types of less toxic, less debilitating and more effective therapies are needed.

Pancreatic cancer:

Carcinoma of the pancreas has had a markedly increased incidence during the past several decades and ranks as the fourth leading cause of cancer death in the United States (American Cancer Society, 2009; Greenlee et al, 2000). Despite the high mortality rate associated with pancreatic cancer, its etiology is poorly understood. Cancer of the exocrine pancreas is rarely curable and has an overall survival (OS) rate of less than 4%[Greenlee et al, 2000]. The highest cure rate occurs if the tumor is truly localized to the pancreas; however, this stage of the disease accounts for fewer than 20% of cases. For those patients with localized disease and small cancers (<2 cm) with no lymph node metastases and no extension beyond the capsule of the pancreas, complete surgical resection can yield actuarial 5-year survival rates of 18% to 24%. (Yeo et al, 1997). Improvements in imaging technology, including spiral computed tomographic scans, magnetic resonance imaging scans, positron emission tomographic scans, endoscopic ultrasound examination, and laparoscopic staging can aid in the diagnosis and the identification of patients with disease that is not amenable to resection. For patients with advanced cancers, the OS rate of all stages is less than 1% at 5 years with most patients dying within 1 year.

No tumor-specific markers exist for pancreatic cancer; markers such as serum CA 19-9 have low specificity. Most patients with pancreatic cancer will have an elevated CA 19-9 at diagnosis. Following or during definitive therapy, the increase of CA 19-9 levels may identify patients with progressive tumor growth. The presence of a normal CA 19-9, however, does not preclude recurrence.

According to the National Cancer Institute (www.cancer.gov/cancerinfo/types/pancreatic), patients with any stage of pancreatic cancer can appropriately be considered candidates for clinical trials because of the poor response to chemotherapy, radiation therapy, and surgery as conventionally used. One such trial is the gemcitabine, docetaxel, capecitabine (GTX) therapy being utilized at Columbia University by [name] and his colleagues (Phase II).

Colorectal cancer:

In contrast to pancreatic cancer, cancer of the colon is a highly treatable and often curable disease when localized to the bowel. Surgery is the primary form of treatment and results in cure in approximately 50% of the patients. Recurrence following surgery is a major problem and is often the ultimate cause of death.

The prognosis of patients with colon cancer is clearly related to the degree of penetration of the tumor through the bowel wall, the presence or absence of nodal involvement, and the presence or absence of distant metastases. Beyond those characteristics, elevated pretreatment serum levels of carcinoembryonic antigen (CEA) have a negative prognostic significance. The fact is, however, that, even with good prognostic factors and aggressive chemotherapy with regimens such as FOLFOX and FOLFIRI, with or without the addition of bevacizumab and cetuximab (the latter for KRAS⁺ patients), many patients become resistant to available chemotherapies and targeted biological therapies. In addition, the other surgical and ablative techniques may no longer be applicable. With liver and lung metastases common problems, and brain metastases less common, but potentially devastating, there clearly is a need for new, more effective therapeutic measures, especially for those patients who do have metastatic spread of their tumors

Among the therapeutic possibilities currently being explored for pancreatic and colorectal cancer, as well as other solid tumors, those that involve cellular biological control mechanisms seem both promising and attractive. Many such modalities-- such as induction of terminal differentiation, enhancement of growth-inhibitory (negative) feedback, selective programmed cell death (apoptosis), targeted insertion of viral or other genes into the proliferating cancer cell, and growth arrest at either the G1-S or G2-M checkpoints of the cell cycle -- all seem to be feasible goals with significant potential for clinical use. Furthermore, recent data suggest that a subpopulation of cells within a tumor, i.e., the so-called cancer stem or progenitor cells, which have been described and characterized in certain tumor types such as those of the brain (glioma series), colon, and breast, may, in fact, be responsible for tumor survival, progression, resistance, and metastasis. Should these observations be verified, these cell populations represent a novel and fundamental target for anti-neoplastic therapy.

The development of truly new and more effective therapeutic approaches to the treatment of neoplastic disease requires a far better understanding of the nature of cancer than we currently have. It is increasingly clear that cancer is not simply the result of a rogue, mutated cell or clone of cells exhibiting unrestricted proliferative and metastatic behavior. Rather, cancer is itself a biological system, in a sense a kind of (undesirable) organ and/or organ system. Furthermore, cancer is not an entirely separate entity within the host, but rather dependent on complex interactions with the host as a whole and its own microenvironment, just as a normal organ is. The local microenvironment may, in fact, aid and abet the neoplastic cells, providing them with blood flow and nutrition, for example. The "normal" host cells in the microenvironment may not be normal at all, but may become incorporated into the structure and workings of the tumor. In other words, the tumor is a heterogeneous collection of interdependent cells, the least desirable of which may be what we think of as the neoplastic cells. Those cells, however, are only part of the story.

The fact that cancer is, in effect, an alternative organ system, suggests that it should be subject to at least some of the same regulatory processes that govern normal, physiologic system function. One such process, the control of proliferation in a normal organ, is quite strict. Although it has long been thought that cancer cells and the tumors they form are not subject to the same regulatory growth-control feedback mechanisms as are normal cells and organs, increasing evidence suggests that they are, in fact, subject to such regulation. Not surprisingly, an important signal in the growth-regulatory process for tumor cells is the mass of tumor present. Tumor growth slows as the mass of both primary and metastatic tumors increase (7-12). Surgeons, for example, have observed that surgical excision of part of a tumor mass can be associated with rapid re-growth of the remaining tumor and/or distant metastases (13,14). De Wys (15) and Fisher et al (16) have demonstrated the same phenomenon in animal models of tumors. We have been able to confirm this ourselves in a mouse tumor model involving the injection of mouse renal adenocarcinoma cells under the renal capsule. In these studies, removal of the primary tumor at an early stage of development of the malignancy has resulted in the appearance of dramatically greater numbers of distal metastases. Taking these various findings into account, it is not unreasonable to argue, as Prehn has done (17), that a promising therapeutic approach to the biological control of tumor growth could consist of "fooling" tumors into sensing that their mass is greater than it actually is, thereby slowing or halting tumor growth.

The proposed cancer treatment to be tested in the Phase II clinical trial outlined in this protocol is based, at least in part, on the concept that tumor growth

can be controlled by tumor mass or signals that indicate that such mass is present. In this case, however, the induction of such signals is brought about not by true tumor mass, but rather by placing cancer cells in a proliferation-restrictive hydrophilic matrix composed of agarose. In brief, cancer cells (in this case, mouse renal adenocarcinoma cells) placed in such a growth-restrictive matrix contained within the structure of a 6-8mm "macrobead" are induced to produce and release signals that can inhibit the proliferation of free cancer cells of the same and different types (and without species specificity) both *in vitro* and *in vivo*. Translated into practical clinical terms, the release of such inhibitory signals from cancer cells in a proliferation-restrictive environment could be useful in the treatment of human cancers.

Based on our continued laboratory and clinical studies with the macrobead approach to the control of the cancerous growth, we can say that the mechanisms by which this is achieved are more complex than the model advocated by Prehn. In fact, the cells that survive to function in the bead have at least some of the properties of cancer stem or progenitor cells. These colonies are comprised of cells that secrete inhibitory factor(s), which, in turn, regulate a variety of processes in the freely growing cancer cells. These affected processes include regulation of the cell-cycle check points (G1S and G2M), DNA synthesis/replication, cell-cell interactions, angiogenesis, cellular metabolism and cytoskeletal function more generally. In other words, the macrobeads themselves constitute an altered, constrained neoplastic system with the capability of influencing the behavior of other, non-constrained neoplastic systems. *In vivo*, these changes are achieved without any evident impairment to date of normal body functions, including that of the immune system. In fact, data from our Phase I clinical trial show that the human immune system is of normal to increased activity after the beads have been placed.

The heterogeneous renal adenocarcinoma cell population initially placed in the agarose matrix of the macrobead undergoes dramatic depopulation followed by dedifferentiation of the surviving cells. Specifically, colonies emerge that contain both cells with stem cell-like properties and cells with other as yet undefined properties. The latter group has features suggestive of the tumor "niches" that have now been described in a range of tumors. These niches represent the bodies that are now postulated to be responsible for tumor generation and survival/perpetuation. They are likely also to be the source of the cells that can break loose and form both local and distant metastases. *In vivo*, niches are composed of cells morphologically and molecularly similar to those seen in the macrobeads, but have the additional feature of being surrounded by an outer coat of fine blood vessels that both nourishes and protects them from host defenses, as well as possibly external therapies. Quite apart from their biological importance in neoplasia, the niches represent a unique endpoint for assessing the anti-neoplastic efficacy of the macrobeads.

While the properties of the cancer stem cells, “niches”, and the macrobeads that contain them are of significant scientific interest, their precise mechanism of anti-tumor action has yet to be fully explored. Genomic studies of the cells within the colonies in the macrobeads show striking up-regulation of certain genes such as CHOPP and GADD45. One or more, or all, of the proteins produced by these and other genes, which can be measured by PCR, can be released into the medium and serve as the postulated signals to the freely-growing cancer cells. Whatever the outcome of this important line of research, however, there is solid evidence in preclinical studies that the macrobeads may yield clinically important results. Preclinical studies in mouse tumor models, both in vivo and in vitro, have indicated statistically significant activity of the macrobeads with respect to suppression of tumor growth. Studies in 45 dogs and cats with the above macrobeads in the treatment of a variety of spontaneous tumors including gastrointestinal lymphoma, prostate cancer and hepatocellular tumors have shown a tumor response rate of at least 50%. Increased activity levels and weight gain have also characterized these animals after RENCA macrobead implantation consistent with an improved quality of life.

New and ongoing in vitro laboratory studies with human tumor cell lines including those with an androgen-independent, docetaxel-resistant human prostate cell line have shown that the macrobeads can slow or stop the proliferation of these cells when no other agents are effective. These in vitro studies, plus in vivo tests with the same tumor line in an immunodeficient mouse tumor model, add further, preclinical support to the trial proposed here. If the macrobeads continue to be effective after cancer cells have developed resistance to all currently available agents, then they could have a place in the clinical treatment of advanced cancers, let alone those at an earlier stage.

The Phase I trial of the cancer macrobeads in the initially targeted 13 subjects with a variety of Stage IV, end-stage, treatment-resistant epithelial-derived tumors has enrolled and implanted 31 subjects to date, 21 more than the original goal of 10. It has demonstrated that the macrobeads are well tolerated when implanted in the human abdominal cavity for periods of up to 24 months. Tumor types evaluated in the safety/toxicity trial have included colorectal carcinoma, gall bladder cancer (cholangiocarcinoma), gastric carcinoma (schirrous type), pancreatic carcinoma, ovarian carcinoma, and non-small cell lung carcinoma. There was no pattern of any consistent adverse effect attributable to the macrobeads. Rather, the problems that did occur were attributable to the disease process itself. Phase I study is closed for the subject accrual and is only open for data analysis.

3 OBJECTIVES

All study objectives will be assessed in each of the two study groups to be enrolled in this clinical trial: subjects with advanced pancreatic cancer and subjects with advanced colorectal cancer.

3.1 Objectives for the advanced colorectal cancer

The objectives for the advanced colorectal cancer, as defined in the Statistical Analysis Plan (SAP), are:

3.1.1 Efficacy

The primary efficacy outcome is post-implantation all-cause mortality, where time to death is defined as the time from the first scan showing disease progression after completion of prior treatment (time of origin, T_0) to death from any cause.

Secondary efficacy outcomes are (if feasible):

- Time from first implantation to death.
- Time from disease Stage IV diagnosis to death.
- Changes from baseline based on Magnetic Resonance Imaging (MRI), computerized tomography (CT) or positron emission tomography (PET)-CT scan, and other appropriate imaging techniques (e.g., sonography, bone scans, other x-rays) as indicated, if feasible.
 - o In primary and/or secondary tumor size (volume, area) and
 - o In state (necrosis, vascularization) on MRI, CT or PET-CT scan, and other appropriate imaging techniques (e.g., sonography, bone scans, other x-rays) as indicated.
- Change from baseline in tumor markers (CEA, CA19-9)
- Changes from baseline in CA125 (as a marker of inflammation)
- Changes from baseline in
 - o Clinician Global Clinical Assessment
 - o Activities of daily living
 - o Symptom rating
 - o Quality of life (QCQ-C30)

- o Pain scale
- o ECOG
- Additional exploratory efficacy outcomes may be analyzed if feasible and will be defined in the CSR.

3.1.2 Safety

Safety outcomes will include:

- Reason for study discontinuation (coming off protocol).
- Incidence of adverse events (AEs).
- Changes from baseline in physical examination parameters, including weight, vital signs, and electrocardiogram (ECG).
- Changes from baseline in laboratory parameters (see section 5.6 of the protocol).
- Changes from baseline in murine antigens skin test.
- Changes from baseline in status of murine leukemia virus as detected by polymerase chain reaction (PCR).

3.1.3 Exploratory

Exploratory outcomes will include presence or absence of circulating tumor cells. An addition to the endpoints for assessing efficacy will be, where possible, when a biopsy is indicated, a careful search for, and identification of, the niches of cancer stem and other cells within the niche bodies of the tumors the macrobeads are being used to treat. Markers of the niche used to identify these cells and study their properties (numbers, integrity of surrounding blood vessels, degree of stress) will include HLA, CD44+, CD133+.

3.2 Objectives for the advanced pancreatic cancer

3.2.1 Primary Objective

To determine the Response Rate (RR), at 2 weeks, 4 weeks, 8 weeks, 3 months, 6 months, 9 months, 12 months or longer as possible, of subjects treated with macrobeads after they have failed standard chemotherapeutic regimens or have decided not to pursue standard or experimental chemotherapy for treatment-resistant, metastatic pancreatic adenocarcinoma, where RR is defined as:

- Evidence of change in primary or secondary tumor size (volume, area) as well as state (necrosis, vascularization, metabolic rate) on PET-CT, as well as MRI and/or CT as appropriate
- Decrease in tumor markers (including CEA and CA 19-9) and specific biochemical parameter levels in plasma/serum
- Stable or improved quality of life as measured by EORTC QLQ-C30, weight, and pain control
- Stable or improved global clinical rating of subject by physician and/or nurse
- Increase in LDH consistent with tumor necrosis (significance of LDH changes will be determined in relation to imaging changes indicative of necrosis)

3.2.2 Secondary Objectives

1. To determine the safety and tolerability of the implantation of the RENCA cancer-cell-containing macrobeads in advanced pancreatic cancer subjects with respect to:
 - The peritoneum: irritation, inflammation, mechanical effects (over a period of at least 3 months);
 - Other intraperitoneal organs (liver, spleen, large and small intestines, kidney, bladder, omentum, etc.);
 - Local and systemic immune response (T and B cell/cellular, antibody responses);
 - Bacterial, viral zoonotic infection (clinical and hematological examination; PCR DNA analysis for viral DNA; specific viral antibodies);
 - Hypersensitivity reactions to murine antigens.
2. To determine progression, defined as the time from the first implantation until the first occurrence of any of the following events
 - a. Death due to any cause, or
 - b. Progression as defined by the presence of the occurrence of any three of the five following events:
 - i. An increase in the levels of tumor markers (e.g., CEA, CA19-9) of 50% from baseline determinations
 - ii. Radiographic progression including increase in primary or metastatic tumor size/volume; increasing metabolic activity of the presenting tumor or of new metastatic lesions on a PET/CT scan after the administration of radio-labeled fluorodeoxyglucose (FDG); and evidence of new metastatic lesions.

- iii. A decrease in the EORTC QLQ-C30 quality of life scale as compared to baseline of more than 25%;
(Above data will also be analyzed with censorship of deaths to further evaluate progression)
3. Determine overall survival (OS)
4. Circulating tumor cells will also be measured

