4.3 Selection of Study Population

4.3.1 Inclusion Criteria:

1. Histologically-confirmed adenocarcinoma of the pancreas, colon, or rectum.
2. Radiographic evidence of metastatic cancer of the colon or rectum
3. The subject has pancreatic cancer that is unresectable or already metastatic or colorectal cancer that has failed available treatment modalities.
4. For the pancreas subjects, he/she may be accepted without prior chemotherapy or with multiple therapies that have failed. The colon and rectal cancer subjects must have failed available chemotherapy/targeted regimens. There is no limit to the number of prior chemotherapeutic regimens.
5. The subject must have evidence of progressive disease defined as at least one of the following:
 - a. Progressive measurable disease: using conventional solid tumor criteria
 - b. Increasing tumor markers and/or activity on PET-CT SUV measurement
6. All clinically significant toxic effects (excluding alopecia) of prior surgery, radiotherapy, or hormonal therapy have resolved to \leq Grade 1 based on the NCI-CTCAE v 3.0, with the exception of peripheral neuropathy, which must have resolved to Grade \leq 2.
7. The subject has an Eastern Cooperative Oncology Group performance status (ECOG PS) of 0-2.
8. The subject has adequate hematologic function (minimum requirements: absolute neutrophil count [ANC] \geq 1500/mL, hemoglobin \geq 9 g/dL, and platelets \geq 100,000/mL).
9. The subject has adequate hepatic function (bilirubin \leq 1.5 times the upper limit of normal (ULN)), aspartate transaminase [AST] and alanine transaminase [ALT] \leq 3 times the ULN, or \leq 5 times the ULN, if liver metastases are present).
10. The subject has adequate renal function (creatinine \leq 2.0 mg/dL)
11. The subject has adequate coagulation function (an international normalized ratio [INR] \leq 1.5 and a partial thromboplastin time [PTT] \leq 5 seconds above the ULN [unless on oral anticoagulant therapy]). Subjects receiving full-dose anticoagulation therapy are eligible provided they meet all other criteria, are on a stable dose of oral anticoagulant or low molecular weight heparin (and if on warfarin have a therapeutic INR between 2 and 3).
12. The subject has a life expectancy of 6 weeks.
13. The subject is male or female and at least 18 years of age. For females of childbearing potential, a negative pregnancy test is required.
14. The subject agrees to use contraceptives (barrier method) while on study, if sexually active.

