- Comprehensive Metabolic Panel with LD, GGT, CRP, direct bilirubin
- Cytokine panel
- CEA, CA 19-9, CA 125
- Circulating Tumor Cell Levels
- Ecotropic murine leukemia virus tests
- Monitoring of adverse events and concomitant medications
- Global clinical assessment
- Quality of life scale
- ECOG and Karnofsky Performance status rating
- Pain scale, if appropriate

5.1.8 Visit 4, Study Day 60 ± 5 days:

The following data will be obtained:

- Vital signs with weight
- Physical examination with brief neurological exam
- CBC with differential WBC, platelet count
- Coagulation profile (PT, PTT and INR)
- Erythrocyte sedimentation rate
- Comprehensive Metabolic Panel with LD, GGT, CRP, direct bilirubin
- Cytokine panel
- CEA, CA 19-9, CA 125

- Circulating Tumor Cell Levels
- Monitoring of adverse events and concomitant medications
- Global clinical assessment
- Quality of life scale
- ECOG and Karnofsky Performance status rating
- Pain scale, if appropriate

5.1.9 Visit 5, Study Day 90 ± 5 days:

The following data will be obtained:

- Vital signs with weight
- Physical examination with brief neurological exam
- CBC with differential WBC, platelet count
- Coagulation profile (PT, PTT and INR)
- Erythrocyte sedimentation rate
- Comprehensive Metabolic Panel with LD, GGT, CRP, direct bilirubin
- Cytokine panel
- CEA, CA 19-9, CA 125
- Circulating Tumor Cell Levels
- Ecotropic murine leukemia virus (immunology, PCR) tests
- Monitoring of adverse events and concomitant medications
- Global clinical assessment
- Quality of life scale
- ECOG and Karnofsky Performance status rating
- Pain scale, if appropriate
- MRI if needed
- PET-CT scan of whole body
- Pregnancy test, females of childbearing potential only
- Urinalysis
- EKG
- CXR
- Cellular immune function [T cells, B cells, Antibodies to common bacteria and viruses (diphtheria, tetanus, mumps, rubella), Quantitative IgG subclass determinations, NK cells count (CD16)]
- Immunoglobulin Levels (IgA, IgG, IgE, IgM)
- Murine allergen skin test, including positive and negative controls

Decision to Proceed with Second Implantation

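### Pancreatic progression (Protocol 3.2.2) requires three of five events but lists only three, and the SAP plans progression outputs without defining the event

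*Protocol*

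**What the plan says.** Secondary objective 2 for pancreatic cancer (Protocol 3.2.2) runs from the first implantation to the first of two events: death from any cause (2.a) or progression (2.b). Progression is "Progression as defined by the presence of the occurrence of any three of the five following events". The items that follow are:

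- i: tumor markers up by 50% from baseline;
- ii: "Radiographic progression including increase in primary or metastatic tumor size/volume; increasing metabolic activity of the presenting tumor or of new metastatic lesions" on FDG PET/CT, together with evidence of new metastatic lesions;
- iii: "A decrease in the EORTC QLQ-C30 quality of life scale as compared to baseline of more than 25" per cent.

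Item iii ends in a semicolon. The next text is a bracketed note, "Above data will also be analyzed with censorship of deaths to further evaluate progression", and then objectives 3 and 4. There is no item iv or v.

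Protocol Appendix 3 (item 7) leaves the analysis of secondary objectives to the SAP. SAP 3.3.1 and 10 do not list progression among the outcomes, and SAP 16.2 has no table for it. SAP 16.3 nevertheless plans several progression-free survival (PFS) figures, and SAP 16.1 plans Listing 16.2.6.4.2, time from first implantation to radiologically evident progression.

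**The concern.** The mismatch sits in the sentence that defines the event. An analyst who trusts the list and one who trusts the count would not be applying the same endpoint, and the second could not apply it at all. The SAP, which should settle the matter, plans outputs for the endpoint without saying what counts as an event, when it is dated or who is censored.

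No hypothesis test depends on this. What is at stake is the use of the results: Protocol 7.1 says the pancreatic data will feed the planning of a controlled Phase IIb protocol. A progression curve whose event was settled after the data were seen is a poor planning input.

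**Working it through.** **1. Try to reproduce the five.**

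| Way of counting | Sum | Outcome |
|---|---|---|
| As numbered: i, ii, iii | 1 + 1 + 1 = 3 | 5 − 3 = 2 events unaccounted for |
| Item ii split into size/volume, metabolic activity and new lesions | 1 + 3 + 1 = 5 | Reaches five, but against the numbering |
| Two further events omitted from the list | 3 + 2 = 5 | Reaches five, but two events are unknown |

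**2. What each count implies.** As numbered, any three means all three, so radiographic progression without both a marker rise and a quality-of-life fall is never an event. With item ii split, imaging findings alone could reach three. If two events are missing, no date can be assigned until they are restored.

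**3. Look for a repair elsewhere.**

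| Place | What it adds |
|---|---|
| Protocol 5.7 | Refers back to Section 3 for the definition |
| Protocol 5.8 | Six criteria: PET-CT/MRI progression, two or more new lesions, symptomatic or ECOG deterioration, weight loss, other cancer-related events needing major intervention, death. It is not a three-of-five rule, and no marker or QLQ-C30 threshold is among the six |
| SAP List of Definitions | No entry for progression |
| SAP 10.1.1 | Censoring rule for time to death only |
| SAP 10.2 | Survival methods for time-to-event outcomes, with the event left generic |

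None of these resolves the count, and 5.8 adds a competing list.

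**4. What the SAP output titles supply.** They distinguish any death from cancer-related death, and they label some outputs as radiographically or radiologically evident. They give no criterion, threshold, event date or censoring rule. None is identified as the deaths-censored analysis promised in 3.2.2.

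**5. Baseline.** Items i and iii are changes from baseline. Protocol 7.2 keeps the baseline from before the first implantation for the whole study, while SAP 6.4.1.2 sets a new one for each implant. The progression rule does not say which applies.

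**6. Does the sample size depend on this?** Protocol Appendix 3 (item 9) bases the original 20 colorectal and 10 pancreatic subjects on precision for progression and toxicity rates, taking a 50% rate as the worst case. The half-width is 1.96 × √(0.5 × 0.5 / n). For n = 20 it is 0.219, against 22 points stated; for n = 10 it is 0.310, against 31 stated. Only n and the assumed rate enter, so the definition of progression does not change these figures.

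**The case against.** The best defense is that the SAP supersedes the protocol's statistical considerations (SAP 1 and 13) and modifies some efficacy parameters because tumor measurements often cannot be obtained (SAP 2). On that view progression was dropped and the PFS figures are leftover shells. SAP 3.3.1 and 10 also allow additional exploratory outcomes to be defined in the clinical study report (CSR). This may well be what happened, but it does not close the gap. The outputs are still planned. The SAP was written for Amendment 10, while the current protocol, Amendment 11, keeps the objective. Deferring the definition to the CSR means choosing it after the data are seen.

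A second defense is that splitting item ii reaches five, so nothing is missing. The numbering i to iii and the word *including* make item ii a single event, so this reading is strained. It cannot be assumed without a correction.

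A third is that two lines were lost in converting the document. No redaction mark appears, and item iii runs straight into the closing note. Loss is therefore unlikely, though not excluded, and the sponsor can settle it from the source file.

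The remaining points stand: the endpoint is secondary, all analyses are exploratory, and the output titles do convey part of the event.

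**Conclusion.** The inconsistency is real and should be corrected before analysis. Its size is a count of three against a stated five, plus a set of SAP outputs with no event definition. The documents support no figure for its effect on PFS, and no direction of bias is claimed.

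Several stronger conclusions might be inferred, and the documents do not support them:

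- **Progression cannot be dated before the Day 90 PET-CT.** SAP 6.4.2 and 6.4.4 treat data as unscheduled only outside the nominal windows (Days 7–21, 23–37, 53–67 and 83–97 after the first implant), and Protocol 5.3 allows CT/MRI as appropriate at every scheduled visit. Death before any scan, possible given the six-week life expectancy criterion, is already an event under 2.a.
- **Most patients could have only death as an event.** Under the numbered reading this is true of a patient with no evaluable post-implant imaging. SAP 2, however, speaks of tumor measurements, while item ii also covers metabolic activity and new lesions. How often all imaging is missing is not stated.
- **The lost events are the global rating and LDH.** Protocol 3.2.1 lists "Stable or improved global clinical rating of subject by physician and/or nurse" and an LDH increase among its response domains, but linking these to 2.b is guesswork. There, an LDH increase counts toward response and is interpreted alongside imaging.
- **The readings give calculable event rates.** That would need component probabilities and their dependence, which the documents do not give.
- **The sample size is undermined.** Step 6 shows otherwise, and SAP 3.4 calls the size practical.
- **Colorectal patients are equally affected.** Section 3 opens with "All study objectives will be assessed in each of the two study groups to be enrolled in this clinical trial", but Section 3.1 sets the colorectal outcomes without progression. The point is confined to the pancreatic objective.

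**What to change.** Before analysis:

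1. In Protocol 3.2.2, restore the missing events or correct the count to match the list. State whether item ii is one event or three, and name the baseline, reconciling Protocol 7.2 with SAP 6.4.1.2.
2. Reconcile Protocol 3.2.2, 5.7 and 5.8 by stating which list defines the endpoint.
3. In the SAP, take one of two routes:
   - Carry over that single definition with event-date and censoring rules for each output. Cover patients without evaluable post-implant imaging, and say which output is the deaths-censored analysis.
   - Delete the PFS figures and Listing 16.2.6.4.2, and explain the departure from protocol objective 2 in the CSR, as SAP 1 requires.

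The cost is wording in the two documents, with no new data. Depending on the route, reported progression times may change or the progression outputs may be dropped.
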